4.4.3 Efficacy

Not applicable.

4.4.4 Derived Other Variables

4.4.4.1 Age for Demographics

The age of a subject in the study is the calendar age.

4.4.4.2 Duration of the Study

The duration of the study is computed in days as follows:

Latest date of all subjects (termination date, last visit date, date of last contact) – earliest date of all subjects (date of visit V01) +1.

4.4.4.3 Subject Duration

The duration of a subject participation in the study is computed as follows:

Maximum (Visit dates, Termination date, Follow-up date, Last contact date) – V01 date + 1.

4.4.5 Baseline Dengue status

The dengue status at baseline is defined as the presence of Abs against at least one dengue serotype in the baseline sample (by dengue 50% plaque reduction neutralization test [PRNT₅₀] in the BL collected at V02 (BL) from all subjects. The baseline dengue status variable will be calculated for each subject as follows:

- Dengue immune subjects at baseline (seropositive) are defined as those subjects with titers ≥ 10 (1/dil) for at least one serotype with the parental dengue virus strain
- Dengue non-immune subjects at baseline (seronegative) are defined as those subjects with titers < 10 (1/dil) (not quantified) for all serotypes with parental dengue virus strains with available “valid” results (i.e. different from missing or ”NR”)
- Otherwise the baseline status will be classified as undetermined and subjects will have their dengue baseline status derived as non-immune.

5 Statistical Methods and Determination of Sample Size

The analysis will be performed under the responsibility of the Sponsor’s Biostatistics platform with the SAS software, version 9.4 or higher (SAS Institute, Cary, North Carolina, USA).

The results of the statistical analysis will be available in the final clinical study report (CSR).

For descriptive purposes, the following statistics will be presented:

Table 5.1: Descriptive statistics produced

Baseline	Categorical data	Number of subjects.
----------	------------------	---------------------

characteristics and follow-up description		Percentage of subjects.
	Continuous data	Mean, standard deviation, quartiles, minimum, and maximum.
Clinical safety results	Categorical data	Solicited: Number and percentage (95% confidence interval [CI]) of subjects. Unsolicited: Number and percentage (95% CIs) of subjects, and number of events.
Immunogenicity results	Categorical data (cutoff)	Number and percentage (95% CIs) of subjects.
	Continuous data (titer / titer ratio)	Log10: Mean and standard deviation. Anti-Log10 (work on Log10 distribution, and anti-Log10 applied): Geometric mean, 95% CI of the geometric mean, quartiles, minimum, and maximum. Graphical representation by Reverse Cumulative Distribution Curve (RCDC).

The CI for the single proportion will be calculated using the exact binomial method (Clopper-Pearson method, quoted by Newcombe (2), i.e., using the inverse of the beta integral with SAS®).

For immunogenicity, assuming that Log10 transformation of the titers / data follows a normal distribution, at first, the mean and the 95% CI will be calculated on Log10 (titers / data) using the usual calculation for normal distribution (using Student's t distribution with n-1 degree of freedom), then antilog transformations will be applied to the results of calculations, in order to provide geometric means (GMs) and their 95% CI.

GM is defined as follows:

$$GM = \left(\prod_{i=1}^n y_i \right)^{1/n} = 10^{\sum_{i=1}^n \log_{10}(y_i) / n}$$

where (y_1, y_2, \dots, y_n) are the observed titers or other data where applicable for each subject.

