#### ***Visit 2 (Month 1; 28 [+14] days after Visit 1)***

The Investigator or designated study personnel will:

- 1) Check the information entered into the DC by interviewing the subject/subject's parent (s)/legally acceptable representative(s) and request information concerning any medical event, serious or not, that may have occurred since Visit 1.
- 2) Review the DC pages.
- 3) Recheck inclusion and exclusion criteria for Group 1.
- 4) Perform a physical examination
- 5) Record the subject's axillary temperature.
- 6) Collect information regarding the subject's medication status since the previous visit.
- 7) For female subjects of childbearing potential, perform a urine pregnancy test.
- 8) Obtain blood sample (see [Section 7.1](#) for detailed instructions regarding the handling of blood samples). Blood is to be taken from the limb opposite to the one that will be used for

---

a It is important to note that, if the attempt(s) to collect blood is (are) unsuccessful, the subject should be given the opportunity for another attempt, even on another day. If ultimately a blood sample cannot be obtained, the reason will be recorded in the eCRF. In that case, and if the subject wants to participate in the trial, he/she will be vaccinated.

vaccination for sequential injection (Group 2), or from the limb opposite to the one that will be used for CYD dengue vaccine injection for concomitant injection (Group 1).

- 9) Review temporary and definitive contraindications to vaccination
- 10) Inject the first dose of CYD dengue vaccine to all subjects.
- 11) Inject Tdap vaccine to subjects in Group 1 on the opposite side (the one who did not receive the CYD dengue vaccine).
- 12) Keep the subject under observation for 30 minutes, and record any immediate AE in the source document.
- 13) Record the date of injection(s), the site and side of injection(s) and the route of administration(s), as well as the dose number of the vaccine(s).
- 14) Give the subject or parent/legally acceptable representative a DC (both Groups).
- 15) Remind the subject or parent/legally acceptable representative to bring back the DC when they return for Visit 3 at a specified date and time.
- 16) Complete the relevant eCRF pages for this visit.

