### **12.2.1 Full Analysis Set**

The FAS is defined as the subset of subjects who received at least one dose of each of the study vaccines (CYD and Tdap). Subjects will be analyzed by the vaccine group to which they were randomized.

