PFDA has not provided a response nor approval for protocol amendment 1. The Sponsor has not received any indication of feedback timelines by the Philippines FDA. Consequently, dengue seropositive subjects included in CYD66, vaccinations have not resumed. At the time of study pause following IDMC recommendation and pending protocol amendment 1 implementation, out of the 688 subjects initially enrolled, 676 subjects (98%) received dengue dose 1, 643 subjects (93%) received dengue dose 2, and none received dengue dose 3. In terms of serostatus at baseline, out of 676 subjects who received the first injection, 629 (93%) were dengue seropositive and 47 (7%) were dengue seronegative. Due to the lack of answer from PFDA, the subjects became out of time window to finalize their vaccination schedule and to complete the last safety follow up call (6 months after the last dose). For this reason, the Sponsor decided to put an end to the CYD66 study with a last visit (considered as the termination visit) of the subjects in order to perform the last safety follow up as originally planned in the protocol. Therefore, no more dengue dose injections were administered to any subjects included in the study since the recommendation of IDMC to stop vaccinating seronegative individuals.

This Statistical Analysis Plan is based on protocol version 1.0 dated 17 March 2016.

2 Trial Objectives

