5.2.1 Full Analysis Set

The FAS is defined as the subset of subjects who received at least one dose of the study vaccines.

Subjects will be analyzed by baseline dengue status and by the group to which they were randomized.

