5.2.2 Per-Protocol Analysis Set

Two PPASs will be defined: one for Tdap (PPT) and one for CYD dengue vaccine after first dose (PPC).

The list of deviations leading to exclusion from the PP populations was adapted to exclude dengue seronegative subjects at baseline from the populations. Further details can be found in Section 5.7

PPT

The subjects presenting with at least one of the following relevant protocol deviations will be excluded from the PPT:

- Subject did not meet all protocol-specified inclusion criteria or met at least one of the protocol-specified exclusion criteria
- Subject had dengue seronegative status at baseline
- Subject did not complete the vaccination schedule (at V02 for Group 1, V01 for Group 2)
- Subject received a vaccine other than the one that he/she was randomized to receive (at V02 for Group 1, V01 for Group 2)
- Administration of vaccine was not done as per-protocol (site and route of administration) (at V02 for Group 1, V01 for Group 2)
- Subject did not receive vaccine in the proper time window (at V02 for Group 1)
- Subject did not provide after Tdap injection a post-dose serology sample in the proper time window or a post-dose serology sample was not drawn (V03 for Group 1, V02 for Group 2)
- Subject received a protocol-prohibited medication (prohibited therapies/medications/vaccines are indicated in the Protocol Section 6.7) (until V03 for Group 1, V01 to V02 for Group 2)
- Subject's serology sample did not produce a valid test result, i.e., no Tdap Ab concentration available (at V03 for Group 1, V02 for Group 2)

PPC

The subjects presenting with at least one of the following relevant protocol deviations will be excluded from the PPC:

- Subject did not meet all protocol-specified inclusion criteria or met at least one of the protocol-specified exclusion criteria
- Subject had dengue seronegative status at baseline
- Subject did not complete the vaccination schedule (at V02 for Group 1, at V01 and V02 for Group 2)
- Subject received a vaccine other than the one that he/she was randomized to receive (at V02 for Group 1, at V01 or V02 for Group 2)

- Administration of vaccine was not done as per-protocol (site and route of administration) (at V02 for Group 1, at V01 and V02 for Group 2)
- Subject did not receive vaccine in the proper time window (at V02 for Group 1 and Group 2)

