5.2.3 Safety Analysis Set

The SafAS is defined as the subjects who have received at least one dose of the study vaccines. All subjects will have their safety analyzed after each dose according to the vaccine they actually received, and after any dose according to the vaccine received at the first dose.

Safety data recorded for a vaccine received out of the protocol design will be excluded from the analysis (and listed separately).

Note: Subject will be included in the “any dose” analysis according to the 1st dose received that corresponds to a protocol group.

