5.2.5 Populations Used in Analyses

The main immunogenicity analyses (non-inferiority tests) will be performed on the per protocol analyses sets PPT and PPC respectively for Tdap and CYD dengue vaccine comparisons For Tdap and will be confirmed on the FAS (only Dengue Immune subjects for CYD dengue vaccine). The subjects will be analyzed by the group to which they were randomized.

All other immunogenicity analyses will be performed on the FAS by baseline dengue status. Subjects will be analyzed by the vaccine group to which they were randomized.

The SafAS will be performed on the safety analysis set by baseline dengue status. Subjects will be analyzed according to the vaccine they actually received.

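### SAP 4.4.5 counts subjects with no valid V02 dengue result as seronegative, so Group 2 subjects who had only Tdap can enter the seronegative rows of descriptive tables untested

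*SAP*

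**What the plan says.** SAP 4.4.5 derives baseline dengue status from the PRNT50 result on the V02 blood sample in both groups. One serotype at or above 10 makes a subject immune (seropositive). All valid results below 10 make the subject non-immune (seronegative). For subjects with no valid result it says: "Otherwise the baseline status will be classified as undetermined and subjects will have their dengue baseline status derived as non-immune".

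Group 2 receives Tdap at V01, 28 days before that sample is due. Entry to the analysis sets does not require the sample. SAP 5.2.1: "The FAS is defined as the subset of subjects who received at least one dose of the study vaccines". SAP 5.2.3: "The SafAS is defined as the subjects who have received at least one dose of the study vaccines".

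The status variable then organises the reporting. SAP 5.2.5: "The SafAS will be performed on the safety analysis set by baseline dengue status". The same section splits the immunogenicity analyses other than the non-inferiority tests by baseline status. SAP 5.2.2 removes a subject from both per-protocol sets (PPT for Tdap, PPC for CYD) on the criterion "Subject had dengue seronegative status at baseline".

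On numbers, SAP section 1 reports 688 enrolled and 676 given CYD dose 1, and continues: "out of 676 subjects who received the first injection, 629 (93%) were dengue seropositive and 47 (7%) were dengue seronegative".

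**The concern.** A Group 2 subject who had Tdap at V01 and gave no V02 sample has no dengue result, yet is in the FAS and SafAS and is labelled non-immune. That subject would count in the seronegative rows of the post-Tdap, any-dose and whole-study safety tables and of the Tdap baseline immunogenicity table. A Group 1 subject who leaves before V02 has had no vaccine and is in neither set, so this can happen in one arm only.

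The rule also disagrees with the rest of the SAP. Section 5.3.2 allows no imputation of missing immunogenicity values. Section 4.4.2.3 codes the indicator for a titer of at least 10 against at least one serotype as Missing when no titer exists. At baseline that indicator and the status variable record the same fact, but an untested subject would be Missing on one and seronegative on the other.

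The seronegative rows are small and describe the population behind the IDMC recommendation, so a reader will take them as tested subjects.

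**Working it through.** **Reproducing the stated figures (SAP section 1).**
- 676/688 = 98.3% (stated 98%).
- 629/676 = 93.0% and 47/676 = 7.0% (stated 93% and 7%).
- 629 + 47 = 676, so no CYD-dosed subject is shown as undetermined.

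**Upper bound.** Subjects without CYD dose 1: 688 - 676 = 12. Only the Group 2 subjects among them who had Tdap and have no V02 sample are affected. Call their number x. The documents do not give x or the split of the 12 by group.

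**Share of all non-immune subjects that would be untested: x/(47 + x).**

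| x | Calculation | Share | Expected truly seropositive, 0.930x |
|---|---|---|---|
| 0 | 0/47 | 0% | 0 |
| 3 | 3/50 | 6.0% | 2.8 |
| 6 | 6/53 | 11.3% | 5.6 |
| 12 | 12/59 | 20.3% | 11.2 |

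The last column assumes that untested subjects have the same seropositivity as the CYD-dosed subjects. The documents do not establish this.

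**Why x = 12 is a ceiling and not an estimate.**
- It needs all 12 undosed subjects to be in Group 2, all to have had Tdap, and none to have a V02 sample. Under 1:1 randomization, with leaving unrelated to group, about 12/2 = 6 would be in Group 2.
- In the Visit 2 steps (Protocol 5.1.4), blood is drawn before contraindications are reviewed. A subject refused CYD at that review would have a V02 sample.
- The Protocol synopsis (Schedule of Study Procedures) and a footnote to the Table of Study Procedures say all subjects completed V01 to V03. Read literally, that gives x = 0. The synopsis also says all subjects received CYD dose 1, which the SAP count of 676 does not bear out, so its wording is loose.

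**What such a subject does and does not enter.** The post-Tdap sample in Group 2 is the V02 sample. Without it there is no post-Tdap concentration, so the subject is outside PPT whatever the status rule says. The subject had no CYD, so is outside PPC and every post-CYD table. With no dengue titer and no post-Tdap concentration, the subject adds nothing to the confirmatory FAS comparisons.

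**CYD-dosed subjects.** One case remains under 4.4.5: a V02 sample drawn but with all four serotypes missing or not reportable. That subject would sit inside the 47 and be excluded from PPT and PPC with the reason recorded as seronegative. The documents do not report any such case.

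**The case against.** The rule is explicit and prespecified, and treating unknown status as non-immune matches the precaution the IDMC asked for. Undetermined subjects are first classified as such, so they stay identifiable, and one complementary safety analysis in SAP 5.1.2.2 names the pooled group as non-immune or undetermined. The effect reaches descriptive tables only and may concern nobody.

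Much of this stands, and it limits the size of the point. The precaution argument does not carry over: it bears on who should receive further doses, and SAP section 1 says none were given after the hold. Naming the pool in one analysis does not separate it in the others.

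A reader might also infer that subjects vaccinated after a failed V02 draw are hidden among the 47. The Protocol does say of a failed draw: "In that case, and if the subject wants to participate in the trial, he/she will be vaccinated". But that footnote is marked at the V01 draw for Group 2 and not at the V02 draw. The synopsis says all subjects gave their 2 (Group 1) or 3 (Group 2) samples before the hold. The sponsor reports that serostatus was determined and communicated, and 629 + 47 accounts for all 676. The documents therefore point to few or no undetermined subjects among those given CYD.

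A second tempting reading is that the SAP departs from the Protocol's FAS, which needs a dose of each vaccine (Protocol 12.2.1). That text is from Amendment 1, while the SAP states that it is based on version 1.0, which is not available here. The difference does not show a departure, and the point does not depend on it.

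**Conclusion.** The point holds as a labelling fault in the derived status variable. As written, SAP 4.4.5 puts a Group 2 subject with Tdap only and no V02 sample into the seronegative rows without a test, against SAP 5.3.2 and 4.4.2.3. It affects at most 12 subjects, probably well below 12 and possibly none. At 3 or 6 they would be 6% or 11% of the non-immune subjects. If the 93% seropositivity carries over to them, most would be mislabelled. The direction of any change in a safety rate is unknown. The non-inferiority tests are not affected. This is a low-priority improvement, justified by its very low cost.

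**What to change.** 1. In SAP 4.4.5, end the quoted sentence at the classification as undetermined and delete the clause that derives these subjects as non-immune. Show undetermined as its own level, with counts per group (zero included), in the FAS and SafAS tables by baseline status.
2. In SAP 5.2.2, write the PPT and PPC exclusion as *seronegative or undetermined dengue status at baseline*. Membership of both sets is then unchanged and the true reason for exclusion is recorded.

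The cost is two short SAP edits and one extra level in a derived variable. No new samples are needed, and the non-inferiority tests stay as planned.

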5.1 Statistical Methods

Non-inferiority testing will only be carried out if the number of evaluable subjects allows a global power of at least 80%. This applies to the co-primary objectives and the secondary objective. Otherwise, analyses will remain descriptive.

5.1.1 Hypotheses and Statistical Methods for Primary Objectives

5.1.1.1 Hypotheses

Non-inferiority on Tdap vaccine

The objective is to demonstrate that the humoral immune response to the Tdap booster dose administered concomitantly with the first dose of CYD dengue vaccine is non-inferior to the humoral immune response to the Tdap booster dose administered alone 28 days before the first dose of CYD dengue vaccine.

Individual hypotheses on Tdap response for each antigen:

A non-inferiority testing approach will be used to compare geometric mean concentrations (GMCs) for PT, FHA, PRN, FIM2+3, 28 days after the booster dose of Tdap, for each antigen “i” based on the following individual hypotheses:

$$H_0^i: GMC_{Group1}^i / GMC_{Group2}^i \leq \frac{1}{\delta} \Leftrightarrow \log_{10}(GMC_{Group1}^i) - \log_{10}(GMC_{Group2}^i) \leq -\log_{10}(\delta)$$

$$H_1^i: GMC_{Group1}^i / GMC_{Group2}^i > \frac{1}{\delta} \Leftrightarrow \log_{10}(GMC_{Group1}^i) - \log_{10}(GMC_{Group2}^i) > -\log_{10}(\delta)$$

with:

i, antigen {PT, FHA, PRN, FIM 2+3}.

δ , non-inferiority limit is set at 1.5, i.e., 0.176 ($=\log_{10} [1.5]$), for each antigen “i”.

Non-inferiority for antigen “i” will be demonstrated if the lower bound of the 2-sided 95% confidence interval (CI) is greater than δ ($\alpha=2.5\%$ one-sided). For each of the 4 antigens, the statistical methodology will be based on the use of the age-stratified two-sided 95% CI of the ratio of GMCs between groups. The age-stratified CI will be calculated using an analysis of variance (ANOVA) model (type II analysis) of \log_{10} -transformed titers. The age groups (9 to 11 years, 12 to 17 years, 18 to 45 years and 46 to 60 years) will be used as the stratifying factor in the model.

Additionally, a non-inferiority testing approach will be used to compare seroprotection rates of T and D, 28 days after the booster dose of Tdap vaccine. Seroprotection is defined as anti-D and anti-T Ab concentration superior to 0.1 IU/mL.

The individual tested hypotheses for the antigen “i” will be as follows:

$$H_0^i: P_{Group1}^i - P_{Group2}^i \leq -\delta$$

$$H_1^i: P_{Group1}^i - P_{Group2}^i > -\delta$$

with:

i, antigen {T, D}

δ , non-inferiority limit is set at 10% for both T and D.

Non-inferiority for antigen “i” will be demonstrated if the lower bound of the 2-sided 95% CI is greater than $-\delta$.

Global hypotheses for non-inferiority on Tdap response:

The global hypotheses are:

H_{0G} : Non inferiority of Tdap booster dose co-administered with the first dose of CYD dengue vaccine versus Tdap booster dose administered alone is not demonstrated for at least one antigen.

H_{1G} : Non-inferiority of Tdap booster dose co-administered with the first dose of CYD dengue vaccine versus Tdap booster dose administered alone is demonstrated for all the antigens.

H_0^G : at least one H_0^i not rejected

H_1^G : all H_0^i are rejected

Non-inferiority on CYD dengue vaccine after 1 dose

The objective is to demonstrate that the humoral immune response to the first dose of CYD dengue vaccine administered concomitantly with Tdap booster dose is non-inferior to the humoral immune response to the first dose of CYD dengue vaccine administered sequentially 28 days after the Tdap booster dose.

Individual hypotheses on CYD response after one dose for each serotype:

A non-inferiority testing approach will be used to compare geometric mean of titers (GMTs), for dengue serotypes 1, 2, 3, and 4, 28 days after the first injection of CYD dengue vaccine between Group 1 and Group 2 for each serotype “i” based on the following individual hypotheses:

$$H_0^i: \text{GMT}_{Group1}^i / \text{GMT}_{Group2}^i \leq \frac{1}{\delta} \Leftrightarrow \log_{10}(\text{GMT}_{Group1}^i) - \log_{10}(\text{GMT}_{Group2}^i) \leq -\log_{10}(\delta)$$

$$H_1^i: \text{GMT}_{Group1}^i / \text{GMT}_{Group2}^i > \frac{1}{\delta} \Leftrightarrow \log_{10}(\text{GMT}_{Group1}^i) - \log_{10}(\text{GMT}_{Group2}^i) > -\log_{10}(\delta)$$

with:

i, serotypes in {1, 2, 3, 4}.

δ , non-inferiority limit is set at 2, i.e., 0.301 ($=\log_{10} [2]$), for each serotype “i”.

Non-inferiority for serotype “i” will be demonstrated if the lower bound of the 2-sided 95% CI is greater than $-\delta$.

Global hypotheses for non-inferiority on CYD response after one dose:

H_0^G : at least one H_0^i not rejected

H_1^G : all H_0^i are rejected

Overall, non-inferiority among the groups will be demonstrated if, for each antigen of Tdap and each serotype of CYD dengue vaccine, the two-sided 95% CI lies above $-\delta$.

